were receiving a higher concentration of Tenofovir DF (two were greater than 120% of the recommended Tenofovir DF dosing regimen), likely due to advanced disease {13569}. A study derived from the same CHIPS cohort evaluated renal toxicities and of those 456 participants on antiretroviral therapy, 20 developed hypophosphatemia (4.4%), 10 of whom were on Tenofovir DF (2.2%). Incidence of hypophosphatemia associated with Tenofovir DF was 4.3/100 person-years and among controls (not exposed to Tenofovir DF) it was 0.9/100 person-years. Recommendations from these studies include longitudinal monitoring of renal function {15423}.

Independent and sponsored studies in recent years have shown that Tenofovir DF use among adults with diagnoses of HBV or HIV carries a modest risk of BMD decreases or acute renal injury compared to placebo or other non-Tenofovir DF containing treatments. Reported decreases in bone mineral density among patients on Tenofovir DF therapy compared to age- and height adjusted bone density scores are rare across all age strata seen in clinical trials and observational studies (GS-US-104-0321, GS-US-104-0352, GS-US-174-0115). Among HIV- and HBV-infected adolescents and children, understanding the longitudinal risk of changes in bone mineral density is critical for managing Tenofovir DF-treatment plans weighed against any possible alterations to bone development in children.

Adverse event data from Gilead-sponsored trials have shown increases in creatinine among 0.2% of subjects, and renal failure in 0.06%. In the Viread® Expanded Access Program, 0.04% of subjects were diagnosed with new onset PRT (including Fanconi syndrome). In pediatric HIV study GS-US-104-0352, 0.05% of patients between 2 and 12 years of age developed PRT; there were no reports of PRT in the parallel trial among adolescents with HIV. Some mediating factors identified in past studies have included advancing age, pre-existing renal insufficiencies, use of known nephrotoxic medications, and low weight. Renal injuries while on Tenofovir DF treatment have been reversible after discontinuation of Tenofovir DF with complete resolution within 4 months for the majority of subjects. The follow up period and sample size of study subjects reporting renal injury have been limited and it is prudent to evaluate these potential risks over a longer timeframe and under real world conditions.

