- DEXA: every 48 weeks from Baseline to Week 96 (3 scans)
- Serum bone chemistry (i.e., calcium, phosphorus, vitamin D levels (25-hydroxy and 1,25 dihydroxyvitamin), PTH, osteocalcin, bone-specific alkaline phosphatase, N and C telopeptides): every 48 weeks
- Serum renal chemistry and urinalysis according to local standards of care

Subjects who permanently discontinue Tenofovir DF will be asked to return for an end of treatment visit within 72 hours of the last dose of Tenofovir DF. Subjects who permanently discontinue Tenofovir DF will be followed for 24 weeks off treatment or up to initiation of local standard of care treatment, whichever occurs first.

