6.1. Subject Enrollment and Treatment Assignment

The study population will consist of HBV-infected adolescents who are between 12 to <16 years of age at the commencement of the study and receiving Tenofovir DF for the treatment of CHB during study treatment. The study population will also be enrolled through one of the approximately 25 participating European clinics across several countries (eg., Bulgaria, Poland, Romania, Italy, France, Spain, and the United Kingdom) projected to commence in June 2015.

Eligibility criteria will include a confirmed diagnosis of HBV infection in subjects who are Tenofovir DF treatment naïve. At screening, adolescent subjects (12 to <16 years of age) with documented chronic hepatitis B (e.g HBsAg-positive for ≥ 6 months), weighing ≥ 35 kg will be eligible for the study.

Subjects must be naïve to Tenofovir DF, but could have received interferon or any oral anti-HBV nucleosides/nucleotide therapy. Subjects experienced on oral anti-HBV nucleoside/nucleotide therapy must have discontinued therapy prior to screening. Subjects must have discontinued interferon at least six months prior to screening.

Data will be collected from subjects prospectively from initial enrollment into the study (baseline) and up to 96 weeks, study completion, loss to follow-up or death, whichever occurs first. Subjects who discontinue Tenofovir DF as a consequence of an AE will be monitored for up to 6 months from the date of the observed AE.

The data will contain medical records, demographics, diagnoses, procedures, medications, and laboratory tests (including DEXA).

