6.5. Assessments for Premature Discontinuation from Study

If a subject discontinues Tenofovir DF (for example, as a result of an AE), every attempt should be made to keep the subject in the study and continue to perform the required study-related follow-up and procedures (see Section 6.6, Criteria for Discontinuation of Study Treatment). If this is not possible or acceptable to the subject or investigator, the subject may be withdrawn from the study.

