7.5.4. Management of Elevated Serum Creatinine and Decreased Creatinine Clearance

- Glomerular filtration rate (estimated creatinine clearance) will be calculated at each visit using the Schwartz Formula for subjects ages 12–17 as follows:

$$\text{Schwartz Formula (mL/min/1.73 m}^2\text{)} = k \times L/\text{Scr}$$

[(k is a proportionality constant, for adolescent females \geq 12 years old is 0.55; and for adolescent males \geq 12 years old is 0.70); L is height in centimeters (cm); and Scr is serum creatinine (mg/dL)]

- If creatinine clearance decreases to < 50 mL/min/1.73 m² (confirmed) at any time during the study, Tenofovir DF should be permanently discontinued, followed by 24 weeks of monthly monitoring in treatment-free follow up if alternative HBV therapy is not initiated.
- Subjects with estimated creatinine clearance < 70 mL/min/1.73 m² and serum creatinine increased ≥ 0.5 mg/dL above baseline should have the serum creatinine and creatinine clearance confirmed by repeating testing within three calendar days of receipt of results and before Tenofovir DF discontinuation, unless such a delay is not consistent with good medical practice.

- Subjects with confirmed estimated creatinine clearance $< 70 \text{ mL/min/1.73 m}^2$ and serum creatinine increased $\geq 0.5 \text{ mg/dL}$ above baseline should have Tenofovir DF discontinued, and the subject should be followed weekly for two weeks. After two weeks, if the estimated creatinine clearance is $\geq 70 \text{ mL/min/1.73 m}^2$, Tenofovir DF may be resumed, with monitoring as described below. If the estimated clearance remains $< 70 \text{ mL/min/1.73 m}^2$, Tenofovir DF should be permanently discontinued, followed by 24 weeks of monthly monitoring in treatment-free follow up if alternative HBV therapy is not initiated.
- The serum creatinine and estimated creatinine clearance should be rechecked within two weeks after restarting treatment to ensure that the subject has stabilized. Once this has been determined, the subject should be evaluated at regularly scheduled study visits.
- If creatinine clearance decreases to $< 70 \text{ mL/min/1.73 m}^2$ (confirmed) following restarting Tenofovir DF treatment, Tenofovir DF should be permanently discontinued, followed by 24 weeks of monthly monitoring in treatment-free follow up if alternative HBV therapy is not initiated.

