7.5.7. Management of ALT Flares

Flares on treatment: Spontaneous exacerbations in CHB are relatively common and are characterised by transient increases in serum ALT. After initiating antiviral therapy, serum ALT may increase in some patients. In patients with compensated liver disease, these increases in serum ALT are generally not accompanied by an increase in serum bilirubin concentrations or hepatic decompensation. Patients with cirrhosis may be at a higher risk for hepatic decompensation following hepatitis exacerbation, and therefore should be monitored closely during therapy.

Flares after treatment discontinuation: Acute exacerbation of hepatitis has also been reported in patients who have discontinued HBV therapy. Post-treatment exacerbations are usually associated with rising HBV DNA, and the majority appears to be self-limited. However, severe exacerbations, including fatalities, have been reported. Hepatic function should be monitored at repeated intervals with both clinical and laboratory follow-up for at least 6 months after

discontinuation of HBV therapy. If appropriate, resumption of HBV therapy may be warranted. In patients with advanced liver disease or cirrhosis, treatment discontinuation is not recommended since post-treatment exacerbation of hepatitis may lead to hepatic decompensation. Patients should be placed on commercially available HBV therapy following study drug discontinuation. Liver flares are especially serious, and sometimes fatal in patients with decompensated liver disease.

On-Treatment ALT Flare and Post-Treatment Exacerbation of Hepatitis are defined as:

- Serum ALT $> 2 \times$ baseline and $> 10 \times$ ULN, with or without associated symptoms OR
- Confirmed ALT elevation (defined as 1-grade shift or $2 \times$ previous value) associated with confirmed changes outside of the normal range in other laboratory parameters suggestive of worsening hepatic function (total bilirubin ≥ 2 mg/dL above baseline, abnormal PT ≥ 2 seconds or INR ≥ 0.5 over baseline, abnormal serum albumin ≥ 1 g/dL below baseline or elevated serum lactate levels (if available), defined as $2 \times$ ULN per the Adult AIDS Clinical Trials Group (AACTG) guidelines).

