- If ALT remains $> 2 \times$ baseline and $> 10 \times$ ULN and the bilirubin or PT values are confirmed at $> 2.5 \times$ ULN or $> 1.5 \times$ ULN, respectively, the investigator should consider discontinuing Tenofovir DF and initiating alternative HBV therapy (see below). However, prior to initiating alternative therapy, medical management of the subject should be discussed with the Gilead Medical Monitor. (Note: Once a subject has started alternative therapy, s/he must be discontinued from the study.)

Elevated Liver Enzymes, Elevated Bilirubin and PT/INR ($>$ Grade 2) Symptomatic Elevated Lactate ($> 2 \times$ ULN) or Asymptomatic Elevated Lactate ($> 4 \times$ ULN)

If ALT/AST values are elevated (i.e., $> 2 \times$ baseline and $> 10 \times$ ULN) and bilirubin or PT values are confirmed at $> 2.5 \times$ ULN or $> 1.5 \times$ ULN, respectively, or lactate levels are increased (symptomatic and $> 2 \times$ ULN or asymptomatic and $> 4 \times$ ULN) the investigator should consider discontinuing Tenofovir DF and initiating alternative HBV treatment. The subject must be monitored weekly for as long as enzyme levels and bilirubin and PT/INR remain elevated or above baseline values. Refer to [Appendix 6](#)

for specific guidelines for the management of symptomatic and asymptomatic hyperlactatemia.

- If the ALT/AST levels return to the baseline level and/or Grade 2 or lower during the first 8 weeks of monitoring, Tenofovir DF may be resumed.
- If the ALT/AST levels, bilirubin, PT/INR or lactate levels remain elevated up through Week 8 or deteriorate at any point, the investigator should consult with the Gilead Medical Monitor.

7.5.7.2. Management of Exacerbation of Hepatitis in Subjects Who Have Discontinued Study Medication (Tenofovir DF)

If laboratory results indicate (1) an ALT elevation $> 2 \times$ baseline and $> 10 \times$ ULN OR (2) abnormal laboratory parameters suggestive of worsening hepatic function (bilirubin ≥ 2 mg/dL above baseline, abnormal PT ≥ 2 secs above baseline, abnormal albumin ≥ 1 g/dL below baseline or elevated lactate levels $> 2 \times$ ULN) along with any ALT elevation (i.e., 1 grade shift or $2 \times$ previous value) and the subject is on no post-study therapy for HBV, the following is recommended:

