
Study Duration
	
Subjects will be treated with TDF for 96 weeks. The duration for a given subject is at least 96 weeks plus 30 days to observe safety outcomes.
 
Subjects who permanently discontinue TDF will be asked to return for an end-of-treatment visit within 72 hours of the last dose of TDF. Subjects who permanently discontinue TDF will be followed for 24 weeks off treatment or up to initiation of active treatment, whichever occurs first.

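### The plan gives conflicting rules on whether follow-up of a renal or bone event continues once a subject who stopped tenofovir DF starts other HBV therapy

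*Protocol*

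**What the plan says.** **Text that ends or withholds follow-up at a switch**

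- Protocol 3.2: a subject who permanently stops "will be followed for 24 weeks off treatment or up to initiation of local standard of care treatment, whichever occurs first". Protocol 6.4.2 to 6.4.6 repeat the rule, with the trigger worded variously as an alternative regimen, active treatment or standard of care.
- SAP 1.2 (Study Duration), repeated in 1.3: such subjects "will be followed for 24 weeks off treatment or up to initiation of active treatment, whichever occurs first".
- Protocol 7.5.4: a permanent stop for reduced creatinine clearance is "followed by 24 weeks of monthly monitoring in treatment-free follow up if alternative HBV therapy is not initiated". The condition appears three times in that section.
- Protocol 7.5.7.1, in a note on managing on-treatment ALT flares: "Once a subject has started alternative therapy, s/he must be discontinued from the study".
- Protocol 7.5.7, in the paragraph on flares after stopping: "Patients should be placed on commercially available HBV therapy following study drug discontinuation".

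**Text without that cut-off**

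- Protocol 6.1: subjects who stop because of an AE "will be monitored for up to 6 months from the date of the observed AE".
- Protocol 6.5: after a stop, "every attempt should be made to keep the subject in the study and continue to perform the required study-related follow-up and procedures".
- Protocol 7.3: bone and renal AEs are to be pursued to resolution or stability where feasible, and the sponsor may ask for longer follow-up.
- Protocol 7.5.3: subjects with related Grade 4 events are followed until the abnormality returns to baseline or is explained.

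**The concern.** Protocol section 2 makes the management and outcome of renal and bone AEs a secondary objective, and SAP Tables 19.6 and 19.7 are planned to report them. Protocol 1.4 presents renal injury as reversible after stopping, "with complete resolution within 4 months for the majority of subjects". That statement can be checked in this study only if events are observed after the drug is stopped.

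The two sets of provisions differ in length, in starting point (end of treatment or date of the AE) and in whether a switch ends them. No order of precedence is given. One site could follow 3.2 and 7.5.4 literally and stop collecting recovery data at the switch. Another could follow 6.1 and 7.3 and continue. An event listed as unresolved could then mean either that it persisted or that nobody was asked to look again.

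**Working it through.** There is no sample size, power or event figure to reproduce on this point. The check sets the provisions side by side and then gives a sense of scale.

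**1. A subject with an unresolved renal or bone AE starts other HBV therapy**

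| Provision | Length | Ends at switch? |
|---|---|---|
| Protocol 3.2, 6.4.2–6.4.6; SAP 1.2, 1.3 | 24 weeks off treatment | Yes |
| Protocol 7.5.4 (renal stop) | 24 weeks, monthly | Applies only without a switch |
| Protocol 7.5.7.1 (ALT-flare section) | – | Study exit |
| Protocol 6.1 | Up to 6 months from the AE | Not stated |
| Protocol 6.5 | Required study follow-up | Not stated |
| Protocol 7.3 | To resolution or stability, if feasible | Not stated |
| Protocol 7.5.3 (related Grade 4) | To baseline or explanation | Not stated |

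Appendix 2 of the Protocol schedules no DEXA or renal chemistry after Week 96, only an AE assessment at 30 days.

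**2. Time covered**

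- 24 weeks: 24 × 7 = 168 days.
- 6 months: 365.25 / 2 ≈ 183 days.
- Cited renal recovery time, 4 months: 365.25 / 3 ≈ 122 days, about 17.4 weeks.

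A full 24 weeks covers the cited recovery time (168 > 122). Under a literal reading of 3.2, a switch before about day 122 does not.

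**3. Whether observed outcomes reach the tables**

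- SAP 2.1 ends the final analysis at last dose + 30 days, which is 122 − 30 = 92 days short of the cited recovery time.
- SAP 7.2 ends laboratory tables for discontinuers at last dose + 7 days: 122 − 7 = 115 days short.
- SAP Table 3-1 nevertheless defines a Follow-up Week 24 window at 155 to 182 days after the last dose.
- Protocol 8.2.1.1 puts treatment-free data in the safety summaries; Protocol 8.6 puts them in listings only.

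Tables 19.6 and 19.7 cover treatment-emergent events. An outcome dated later might be carried with the event record, but the SAP does not say so.

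**4. Scale**

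Protocol 1.4 reports that 4 of 89 children in an HIV trial stopped for suspected renal tubulopathy: 4/89 = 4.5%. If that rate applied here:

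- 100 planned: 100 × 4/89 ≈ 4.5 stops; chance of at least one = 1 − (85/89)^100 ≈ 99%.
- 30 enrolled: 30 × 4/89 ≈ 1.3 stops; chance of at least one = 1 − (85/89)^30 ≈ 75%.

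The same section reports no renal adverse drug reactions by Week 72 in the adolescent HBV trial, so the true number could be lower. The documents give neither a rate nor a timing of switching, so outcomes lost could range from zero to every stop.

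**The case against.** The strongest reply is that 3.2 sets general follow-up while 6.1 and 7.3 govern adverse events. On that reading a switch does not end follow-up of a bone or renal AE. The reading is reasonable, but no section states it. 7.3 is qualified by feasibility, 6.1 names no assessments, and 7.5.4 applies the no-switch condition specifically to renal stops.

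A reader might go further and infer that outcomes after a switch will go unobserved, or that a promptly switched subject has no follow-up at all. The documents do not support that. Besides 6.1, 6.5, 7.3 and 7.5.3, they require an end-of-treatment visit within 72 hours of the last dose and an AE assessment at 30 days. The sentences on placing patients on HBV therapy and on study exit also sit in the ALT-flare sections and are not stated as rules for renal or bone stops.

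A reader might also infer that about half of the outcome data would be lost. That has no source: the 4 to 5 events in Protocol 8.9 are expected adverse drug reactions, not discontinuations, and no switching rate is given. Nor does any passage show that switching tracks the severity of the renal or bone event, so a severity-linked bias is possible but not established.

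Finally, SAP 1.4 and 2.1 report that the study closed with 30 enrolled, two completing 96 weeks, and a descriptive analysis. This lowers the practical weight. It leaves open how the recorded outcomes are to be labelled and tabulated.

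**Conclusion.** The conflict stands in current text and is unresolved. The outcome of a renal or bone AE still open when other HBV therapy starts may go unrecorded, depending on which section a site followed. If recorded late, it may fall outside the SAP's windows. The loss cannot be quantified and lies between none and all of the stops. The figures of about 4.5 stops per 100 subjects and 1.3 in 30 are for scale only. They assume that the stopping rate of a paediatric HIV trial with 144 weeks of treatment carries over to this HBV population, where most subjects had shorter exposure. The point concerns outcome data collection and reporting; it is no judgement on how long a subject should be followed clinically or when other therapy should start.

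**What to change.** 1. Reconcile Protocol 3.2, 6.1, 6.4.2 to 6.4.6, 6.5, 7.3, 7.5.3, 7.5.4, 7.5.7 and 7.5.7.1 with SAP 1.2 and 1.3. State which passage governs outcome data collection for unresolved renal and bone AEs, and use one term for the therapy that triggers any cut-off. The choice of clinical rule stays with the sponsor and investigators.
2. As data collection only, record the AE outcome, available routine-care results and the start date of any other HBV therapy.
3. In SAP Tables 19.6 and 19.7, show outcome by whether other therapy was started, so that an event unresolved at last contact is distinct from one whose follow-up ended at a switch.
4. Align the SAP windows (last dose + 30 days in 2.1, + 7 days in 7.2) and settle Protocol 8.2.1.1 against 8.6, so that outcomes observed after stopping reach those tables.

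The cost is wording, a few extra CRF entries and one added split in two tables. Recovery seen while on another drug must be labelled as such. With the study closed, items 3 and 4 remain usable for the data in hand.

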3.3. Study Treatments

The proposed study is an open-label trial of 300mg oral Tenofovir DF which is equivalent to 245mg Tenofovir disoproxil, taken once daily. Tenofovir DF is packaged in white, high-density polyethylene (HDPE) bottles with a white child resistant cap. There are 30 tablets per bottle. Each bottle also contains silica gel as a desiccant to protect the product from humidity and fiber packing to protect the product during handling and shipping.

During Weeks 0 to 96, subjects will be provided with sufficient supplies for 12 weeks of dosing. At a minimum, each bottle will be labeled with a lot number, the protocol number, administration instructions, storage instructions, expiration date, Sponsor name and address. Additional information will be included according to the requirements of the protocol and local law.

Tenofovir DF will be supplied by Gilead as per its current commercial tablet formulation for the EU (300mg Tenofovir DF) for patients greater than 35 kg. There will be no difference in

medication formulation or frequency as per Tenofovir DF SmPC among subjects assigned to either Group 1 or Group 2.

3.4. Duration of Treatment

Subjects will be treated with Tenofovir DF therapy for 96 weeks (each subject will receive a total of 96 weeks of Tenofovir DF treatment). Tenofovir DF is currently approved for use in patients across all specified study countries with participating study clinics aged 12 years of age and up.

3.5. Discontinuation Criteria

Treatment medication may be discontinued in the following instances:

- Intercurrent illness that would, in the judgment of the investigator, affect assessments of clinical status to a significant degree
- Unacceptable toxicity, as defined in the toxicity management section of the protocol, or toxicity that, in the judgment of the investigator, compromises the ability to continue study-specific procedures or is considered to not be in the subject's best interest
- Therapeutic failure
- Subject or legal guardian requests to discontinue for any reason
- Subject non-compliance with taking Tenofovir DF or sustained inability to adhere to Tenofovir DF treatment plan
- Pregnancy during the study
- Discontinuation of the study at the request of Gilead Sciences, regulatory agency or an IEC

3.6. Source Data

Source data will include sequential notes containing at least the following information for each subject:

- Subject identification (name, date of birth, gender)
- Documentation that subject meets eligibility criteria, i.e., history, physical examination and confirmation of diagnosis to support inclusion and exclusion criteria
- Participation in study (including study number)
- Study discussed and date of informed consent
- Dates of all visits

- Documentation that protocol specific procedures were performed
- Results of monitored parameters, as required by the protocol
- Start and end date of Tenofovir DF (preferably with drug dispensing information)
- Record of all AEs and other safety parameters (start and end date, and preferably including causality and intensity);
- Concomitant medications (including start and end dates, dose if relevant; dose changes)
- Date of study completion and reason for early discontinuation, if applicable

All clinical study documents must be retained by the investigator until at least 2 years after the investigation is discontinued and regulatory authorities have been notified. Investigators may be required to retain documents longer if required by applicable regulatory requirements, by local regulations, or by an agreement with Gilead Sciences. The investigator must notify Gilead Sciences before destroying any clinical study records.

Should the investigator wish to assign the study records to another party or move them to another location, Gilead Sciences must be notified in advance. If the investigator cannot guarantee this archiving requirement at the study site for any or all of the documents, special arrangements must be made between the investigator and Gilead Sciences to store these in sealed containers outside of the site so that they can be returned sealed to the investigator in case of a regulatory audit. When source documents are required for the continued care of the subject, appropriate copies should be made for storage outside of the site.

